5.5.2.3 Immunogenicity Analyses

All immunogenicity analyses will be performed using the Safety Analysis Set.

The percentage and frequency of occurrences will be calculated for serum anti-E6011 antibodies and E6011-induced anti-E6011 antibodies by treatment group and time point. If anti-E6011 antibody develops, the frequency and percentage of any anti-E6011 antibody neutralization activity and isotypes will be calculated.

These are analyzed by Week 84.

Subject data listings will be provided.

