The last subject entered the Extension Phase (open-label) in March 2018, and all subjects had completed 52 weeks of treatment with E6011 by March 2019. Consequently, it was

considered unnecessary to conduct any non-safety assessments after March 2019, and the protocol will be revised to Version 6.

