9.5.1.4 Pharmacokinetic, Pharmacogenomic, Biomarker, and Immunogenicity Assessments

After the date Version 6 of the protocol is approved by IRB, it is unnecessary to conduct assessments for pharmacokinetic, pharmacogenomic, biomarker, and immunogenicity. However, pharmacokinetic and immunogenicity assessments will be conducted at discontinuation.

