- a. Study drug will be administered upon completion of all the planned investigations (except for injection site findings) on the day.
- b. To measure height only at the Screening Phase and W52.
- c. To examine injection site findings after study drug administration.
- d. To perform pregnancy test in women of childbearing potential. On-site test conducted at the Observation Phase only.
- e. If any postdose abnormality is observed in neurological examination, head MRI (T1-weighted image, FLAIR image, diffusion-weighted image) will be performed within 2 weeks along with consultation to a neurologist.
- f. The interval between study treatments is at least 7 days (at least 6 days between treatments)
- g. Administration of study drug at Week 24 is done in an open-label manner.
- h. W52+2n: W54, 58, 62, 66, 70, 74, 78, 82, 86, 90, 94, 98, 102
- i. W52+4n: W56, 60, 68, 72, 80, 84, 92, 96
- j. Basically performed at study discontinuation, and a missing value is permissible only when collection of the sample is difficult due to abrupt discontinuation.
- k. Will only be conducted if blood sample is judged to be feasible at the visit.
- l. After the date Version 6 of the protocol is approved by IRB, applicable assessments will not be conducted. However, assessments of serum E6011 concentration and serum anti-E6011 antibody will be conducted at discontinuation.

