Immunocytes such as blood CX3CR1-positive cells	5 mL		once	4 times	once ^c	once ^d
Each Phase		52.0 mL	41.8 mL	225.6 mL	591.8 mL	21 mL
Screening to Week 24			319.4 mL			
Screening to Week 104			911.2 mL			
Screening to the Follow-up Phase			932.2 mL			

a: Blood collections for these items (inside the brackets) are included in those for the items just above.

b: The volume of blood sample is 5 mL at the time point for assessing both serum E6011 concentration and serum anti-E6011 antibody and 2 mL at the time point for assessing serum E6011 concentration only.

c: Twice for subjects who discontinue treatment later than Week 52

d: Will only be conducted if blood collection is judged to be feasible at the visit.

Overview of Protocol Amendment between Ver. 5 and Ver. 6

A Dose Response Study of E6011 in Subjects with Rheumatoid Arthritis Inadequately Responding to Methotrexate

(The parts of change: underline)

Protocol body

Pertinent page	Before Amendment (Ver. 5, August 31,2018)	After Amendment (Ver. 6, March 25, 2019)	Reason for Amendment
P7, 2. CLINICAL PROTOCOL SYNOPSIS Concomitant Drug/Therapy P31, 9.4.7.1.2 Restricted Concomitant Drugs	(no text)	
<Restricted Concomitant Drugs>
 
After the date Version 6 of the protocol is approved by IRB, dose reduction, dose interruption, dose increase following the dose reduction (up to the initial dose level), and restarting administration after interruption will be allowed for MTX, folic acid, corticosteroids, or herbal medicine indicated for RA).
 
There will be no restrictions in using NSAIDs (oral, suppository, or topical).
	Because it was considered unnecessary to conduct any non-safety assessments
P8, 2. CLINICAL PROTOCOL SYNOPSIS Assessments	(no text)	
After the date Version 6 of the protocol is approved by IRB, it is unnecessary to conduct assessments other than <safety>.
	Because it was considered unnecessary to conduct any non-safety assessments
P19, 7. INTRODUCTION	(no text)	
The last subject entered the Extension Phase (open-label) in March 2018, and all subjects had completed 52 weeks of treatment with E6011 by March 2019. Consequently, it was considered unnecessary to conduct any non-safety assessments after March 2019, and the protocol will be revised to Version 6.
	Because it was considered unnecessary to conduct any non-safety assessments

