7 CHANGES IN THE PLANNED ANALYSES

Changes in the planned analyses for protocol are as follows:

- Based on the protocol amendment Version 6, all efficacy results will be summarized until week 84.
- Regarding the PK analysis for extension phase, only listing will be created.

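### The SAP stops the anti-E6011 antibody tables at Week 84, leaving out Week 88-104 visits and most discontinuation samples kept by protocol Version 6, and does not declare this as a change

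*SAP*

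**What the plan says.** SAP 5.5.2.3 uses the Safety Analysis Set and plans frequencies and percentages for "serum anti-E6011 antibodies and E6011-induced anti-E6011 antibodies by treatment group and time point". If antibodies develop, neutralizing activity and isotype are also counted. Two short statements follow: "These are analyzed by Week 84" and "Subject data listings will be provided".

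Other places bear on that limit:

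- **SAP 5.2.1** defines the Safety Analysis Set by a dose and a safety assessment between Week 24 and Week 104.
- **SAP Table 8.8** gives antibody visit windows every 4 weeks to Week 104. It has no row for discontinuation, so results are placed by date.
- **SAP 3 and 7** tie Week 84 to Version 6, but for efficacy: "all efficacy results will be summarized until week 84". The only other change listed in SAP 7 is that Extension PK data will be listed only.
- **Protocol 9.7.1.9** plans Extension immunogenicity analyses like those of the Treatment Phase, with no Week 84 limit.
- **Protocol 9.5.1.4** (Version 6) stops routine antibody sampling after IRB approval, with an exception: "However, pharmacokinetic and immunogenicity assessments will be conducted at discontinuation". The notes to Table 4 in protocol 9.5.2.1 repeat it: "assessments of serum E6011 concentration and serum anti-E6011 antibody will be conducted at discontinuation".

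**The concern.** Week 84 is explained by the end of efficacy assessments. That explanation does not cover antibody samples that Version 6 chose to keep, or scheduled samples already taken at Weeks 88-104 before Version 6 took effect. The SAP gives no separate reason for cutting the antibody tables and does not list the cut as a departure from the protocol.

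Immunogenicity is a secondary objective. The results affected are the late ones: long-exposure visits, and samples from subjects who stop late. Version 6 also added insufficient efficacy, as judged by the investigator, as a ground for withdrawal (protocol 9.3.3), so antibody status in those subjects is of natural interest. A listing shows the individual results but gives no frequency or percentage.

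**Working it through.** **1. Scheduled visits.** Protocol Table 5 states 20 antibody samples in the Extension Phase. Table 4 has visits every 4 weeks from Week 28 to Week 104: (104 - 28)/4 + 1 = 20, which reproduces the figure. Visits after Week 84 are Weeks 88, 92, 96, 100 and 104, so 5 of 20 (25%) leave the tables and 15 remain.

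**2. Where the Week 84 window ends.** Table 8.8 takes the first-dose date + 84 × 7 = 588 days and closes the window before 588 + 14 = 602 days. A discontinuation sample before that point falls in a tabulated window. One at 602 days or later does not.

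**3. How far along subjects were.** Version 6 is dated 25 March 2019; IRB approval dates are not given. The protocol Introduction says that the last subject entered the Extension in March 2018 and that "all subjects had completed 52 weeks of treatment with E6011 by March 2019".
- Last first dose: 1 to 31 March 2018 minus 168 days = 14 September to 14 October 2017. That subject was at Week 75.3 to 79.6 on 25 March 2019.
- Reached Week 104 by then: first dose by 25 March 2019 - 728 days = 27 March 2017.
- Reached Week 88: first dose by 25 March 2019 - 616 days = 17 July 2017.
- Past the Week 84 window: first dose by 25 March 2019 - 602 days = 31 July 2017.

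**4. Share of enrolled subjects with late visits.** No accrual curve is given. Assume even accrual from 15 October or 1 December 2016 to 14 September or 14 October 2017, and no dropout.

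| Start | End | Accrual days | Reached Week 88 | Reached Week 104 |
|---|---|---|---|---|
| 15 Oct 2016 | 14 Sep 2017 | 334 | 275/334 = 82% | 163/334 = 49% |
| 15 Oct 2016 | 14 Oct 2017 | 364 | 275/364 = 76% | 163/364 = 45% |
| 1 Dec 2016 | 14 Sep 2017 | 287 | 228/287 = 79% | 116/287 = 40% |
| 1 Dec 2016 | 14 Oct 2017 | 317 | 228/317 = 72% | 116/317 = 37% |

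**5. Who could still give a Version 6 discontinuation sample.** Only subjects not yet at Week 104, that is, first dosed after 27 March 2017. That span is 171 days (to 14 September) or 201 days (to 14 October). First doses from 27 March to 31 July 2017 cover 728 - 602 = 126 days. The share already past the window is 126/201 = 63% to 126/171 = 74%.

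**6. Follow-up time.** The remaining subjects move past the window as they continue. Let a be the study week of the last-enrolled subject at IRB approval. With even accrual and a constant discontinuation hazard, the share of remaining follow-up after Week 86 (602/7) is 1 - (86 - a)²/(104 - a)². For a = 75.3 this is 1 - 10.7²/28.7² = 86%. With IRB delays of 0 to 8 weeks and a starting value of 75.3 to 79.6, the range is 86% to 100%.

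**The case against.** A common cut is defensible for by-visit tables. Scheduled sampling stopped under Version 6, so denominators after Week 84 would depend on enrolment date. The protocol itself plans antibody frequencies by time point (9.7.1.7.2), so the SAP follows it in not naming an ever-positive proportion. The listings carry no limit of their own, and the table shells are in a separate document. These are descriptive open-label summaries, and the primary analysis is untouched. All of this stands. It supports keeping the by-visit tables as they are. It does not explain the silence in SAP 7 or the absence of any summary that uses the kept samples.

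Three stronger readings are tempting and not supported:

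- **That the cut understates antibody incidence.** Stopping at Week 84 leaves every percentage up to Week 84 unchanged. Only an ever-positive count could be lower.
- **That antibody status in subjects who stop is removed.** Sampling at discontinuation applies throughout the Treatment and Extension Phases, and samples before 602 days still enter by date window.
- **That the 72-82% who had reached Week 88 all lose a Version 6 discontinuation sample.** That group includes the 37-49% who had already reached Week 104 and could not give one.

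**Conclusion.** The point holds as a gap in reconciliation and reporting. The Week 84 limit on antibody tables conflicts with Table 8.8, the Safety Analysis Set and protocol 9.7.1.9, and is undeclared. It takes 5 of 20 scheduled Extension visits and all discontinuation samples from 602 days onward out of the summaries.

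That most Version 6 discontinuation samples fall outside the tables is an inference. It rests on the assumed even accrual and, for the 86-100% range, on a constant hazard and the assumed IRB delay; the documents give no counts. An ever-positive proportion limited to Week 84 cannot exceed the one from all data and may be lower. The difference cannot be computed, because the documents give no antibody rates, and it may be zero. This is a cheap improvement to how a secondary objective is answered.

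**What to change.** In SAP 5.5.2.3, keep the by-visit tables to Week 84 and add one per-subject table:

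- Number and percentage of subjects with at least one positive, and at least one E6011-induced positive, post-dose sample, with neutralizing activity and isotype.
- All samples to Week 104 and all discontinuation samples, whatever the visit window.
- Denominators and time on E6011 (which starts at Week 24 for subjects randomized to placebo).
- A statement that the analysis set includes only subjects dosed and assessed after Week 24, so the proportion is conditional on entering the Extension.

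In SAP 7, declare the Week 84 by-visit cut for immunogenicity alongside the efficacy cut.

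The cost is SAP wording and one more table from data already collected. The downside is unequal follow-up between early and late enrollees, which is why time on E6011 has to be shown beside the proportions.

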5.6 Safety Analyses

All safety analyses will be performed on the Safety Analysis Set. Safety data, presented by treatment group, will be summarized on an “as treated” basis using descriptive statistics (eg, n, mean, SD, median, minimum, maximum for continuous variables; n [%] for categorical variables). Safety variables include treatment-emergent adverse events (TEAEs), clinical laboratory parameters, vital signs, 12-lead ECG results, chest x-ray, neurological findings, and blood CD4 positive cell count. Day 1 for all safety analyses will be defined as the date of the first dose of study drug.

5.6.1 Extent of Exposure

The extent of exposure to study drug will be characterized by duration of exposure, number of injection dose and study medication compliance for each treatment group. Definition of analysis items are as follows:

- Duration of exposure (weeks) = (Date of Last Dose - Date of First Dose + 14) / 7
- Number of Injection = Count of records with non-zero treatment
- Study Medication Compliance (%) = Number of Injection / Number of Expected Injection * 100

Subject data listings will be provided.

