9.5.1.5.1 ADVERSE EVENTS AND EVENTS ASSOCIATED WITH SPECIAL SITUATIONS

An adverse event (AE) is any untoward medical occurrence in a patient or clinical investigation subject administered an investigational product. An AE does not necessarily have a causal relationship with the medicinal product. For this study, the study drugs are E6011 and placebo.

The criteria for identifying AEs in this study are:

- Any unfavorable and unintended sign (including an abnormal laboratory finding), symptom, or disease temporally associated with the use of an investigational product, whether or not considered related to the investigational product (Note: Every sign or symptom should not be listed as a separate AE if the applicable disease [diagnosis] is being reported as an AE)
- Any new disease or exacerbation of an existing disease
- Any deterioration in nonprotocol-required measurements of a laboratory value or other clinical test (eg, ECG or x-ray) that results in symptoms, a change in treatment, or discontinuation of study drug
- Recurrence of an intermittent medical condition (eg, headache) not present pretreatment (Baseline)
- An abnormal laboratory test result should be considered an AE if the identified laboratory abnormality leads to any type of intervention, withdrawal of study drug, or withholding of study drug, whether prescribed in the protocol or not

However, worsening of the primary disease (RA) is not considered an AE unless the symptom aggravated unexpectedly (slight change of RA condition is captured under efficacy assessments as disease progression rather than as an AE).

It is the responsibility of the investigator to review all laboratory findings in all subjects and determine if they constitute an AE.

All AEs observed during the study will be reported on the CRF. All AEs, regardless of relationship to study drug or procedure, must be collected during the time the subject signed the informed consent and 70 days after the subject's last dose. Subjects who failed screening in Screening or Observation Phase primarily due to AE(s), such AE(s) and seriousness must be recorded in the CRF.

Any laboratory abnormality considered to constitute an AE will be reported on the CRF. Abnormal laboratory values are listed as separate AEs if they are considered to be part of the clinical syndrome that is being reported as an AE. Medical and scientific judgment is exercised in deciding whether an isolated laboratory abnormality is classified as an AE.

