5.6.2 Adverse Events

The AE verbatim descriptions (investigator terms from the CRF) will be classified into standardized medical terminology using the Medical Dictionary for Regulatory Activities (MedDRA). Adverse events will be coded to the MedDRA (Version 19.1 or higher) lower level term (LLT) closest to the verbatim term. The linked MedDRA preferred term (PT) and primary system organ class (SOC) are also captured in the database. A treatment-emergent adverse event (TEAE) is defined as an AE that emerges during treatment, having been absent at pretreatment (Baseline) or

- Reemerges during treatment, having been present at pretreatment (Baseline) but stopped before treatment, or
- Worsens in severity during treatment relative to the pretreatment state, when the AE is continuous.

Only those AEs that are treatment-emergent will be included in summary tables.

A subject will be counted only once within an SOC and PT, even if the subject experienced more than 1 TEAE within a specific SOC and PT.

The TEAEs will be summarized by treatment group and E6011 overall. The incidence of follow TEAEs will be reported as the number (percentage) of subjects with TEAEs by SOC and PT:

- TEAEs
- TEAEs by maximum intensity
- Serious TEAEs
- TEAEs leading to study drug withdrawn
- TEAEs leading to interruption of study drug
- TEAEs leading to reduction from study drug
- Treatment Related, TEAEs
- Treatment Related, TEAEs by maximum grade
- Treatment Related, Serious TEAEs
- Treatment Related, TEAEs leading to study drug withdrawn
- Treatment Related, TEAEs leading to interruption of study drug
- Treatment Related, TEAEs leading to reduction from study drug

In the analysis, the AEs emerged until 70 days after the last dose are intended

Subject data listings of All AEs, SAEs, AEs leading to death, leading to study drug withdrawn or leading to interruption from study drug will be provided.

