5.6.3 Laboratory Values

Laboratory results will be summarized using Système International (SI) units. For quantitative parameters listed in [protocol Section 9.5.1.5.3](#), the actual value and the change from baseline to each postbaseline visit will be summarized by visit and treatment group using descriptive statistics. Qualitative parameters listed in protocol Section 9.5.1.5.3 will be summarized using frequencies (number and percentage of subjects), and changes from baseline to each postbaseline visit and to end of treatment will be reported using shift tables. Percentages will be based on the number of subjects with both nonmissing baseline and relevant postbaseline results.

Laboratory test results will be assigned a low/normal/high (LNH) classification according to whether the value was below (L), within (N), or above (H) the laboratory parameter's reference

range. Within-treatment comparisons for each laboratory parameter will be based on 3-by-3 tables (shift tables) that compare the baseline LNH classification to the LNH classification at each postbaseline visit and at the end of treatment. Similar shift tables will be used to compare the baseline LNH classification to the LNH classification for the highest and lowest value during the study.

The Sponsor's Grading for Laboratory Values using CTCAE v4.0 presents the criteria that will be used to identify subjects with treatment-emergent markedly abnormal laboratory values (TEMAVs). Except for phosphate, a TEMA is defined as a postbaseline value with an increase from baseline to a grade of 2 or higher. For phosphate, a TEMA is defined as a postbaseline value with an increase from baseline to a grade of 3 or higher. When displaying the incidence of TEMAVs, each subject will be counted once in the laboratory parameter high and in the laboratory parameter low categories, as applicable.

Laboratory results versus visit by treatment group will be displayed using box-plot.

Subject data listings of Laboratory test results and TEMA will be provided.

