8 DEFINITIONS AND CONVENTIONS FOR DATA HANDLING

8.1 Baseline, Time Windows for statistical analyses

8.1.1 Definition of baseline value

The baseline value was defined as the most recent value reported just before first dosing.

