8.3.3 Adverse Events

Imputation rule for adverse event start date is as follows:

- Year and Month are not missing but Day is missing
 - Year and Month are the same as year and month of the earliest among non-missing values of first dosing date of study Treatment and imputed AE end date: The earliest among non-missing values of first dosing date of study Treatment and imputed AE end date
 - Year and Month are not the same as year and month of the earliest among non-missing values of first dosing date of study Treatment and imputed AE end date: Year and Month as reported on CRF, Day as 1st
- Year is not missing but Month and Day are missing
 - Year is the same as year of the earliest among non-missing values of first dosing date of study Treatment and imputed AE end date: The earliest among non-missing values of first dosing date of study Treatment and imputed AE end date
 - Year is not the same as year of the earliest among non-missing values of first dosing date of study Treatment and imputed AE end date: Year as reported on CRF, Month and Day as January 1st
- Completely missing: First dosing date or imputed AE end date, which is earlier

Imputation rule for adverse event end date is as follows:

- Outcome is ‘fatal’ and End Date is not complete date: Date of death
- Outcome is ‘fatal’ and End Date is complete date
 - different from the date of death: Confirm to CDM
 - same as the date of death: Date of death
- Outcome is not ‘fatal’ and date of death is not missing
 - Year and Month are the same as the year and month of date of death: Date of death
 - Year and Month are not the same as the year and month of date of death: Year and Month as reported on CRF, Day as the last day of the month
 - Year is the same as the year of date of death: Date of death
 - Year is not the same as the year of date of death: Year as reported on CRF, Month and Day as December 31st
 - Completely missing: Date of death
- Outcome is not ‘fatal’ and date of death is missing

- Year and Month are not missing but Day is missing: Year and Month as reported on CRF, Day as the last day of the month
- Year is not missing but Month and Day are missing, and Year is before the Year of date of discontinuation from study: Year as reported on CRF, Month and Day as December 31st
- Year is not missing but Month and Day are missing, and Year is same as the Year of date of discontinuation from study: Date of discontinuation from study

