13.2 Sponsor's Grading for Determining Markedly Abnormal Laboratory Results

Except for phosphate, a TEMAV is defined as a postbaseline value with an increase from baseline to a grade of 2 or higher. For phosphate, a TEMAV is defined as a postbaseline value with an increase from baseline to a grade of 3 or higher.

SIGNATURE PAGE

Author:

PPD

Date

Approval:

PPD

24 May 2020

Date

PPD

Date

Neurology Business Group

PPD

Date

SIGNATURE PAGE

Author:

PPD

Date

Approval:

PPD

Date

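### For placebo-randomized subjects, the extension SAP starts exposure, safety baseline and emergent events at the first placebo dose, and it leaves the E6011 overall column undefined

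*SAP*

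**What the plan says.** **Anchors.** SAP 5.6 sets one Day 1 for all safety analyses, the first dose of study drug. SAP 5.6.1 gives "Duration of exposure (weeks) = (Date of Last Dose - Date of First Dose + 14) / 7", and SAP 8.1.1 says "The baseline value was defined as the most recent value reported just before first dosing". None of the three mentions E6011 or the Extension Phase. Protocol 9.5.1.5.1 states: "For this study, the study drugs are E6011 and placebo".

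**Events.** SAP 5.6.2 counts an adverse event as treatment-emergent (TEAE) if it appears or worsens during treatment relative to the pretreatment state. The only dated limit is at the end: "In the analysis, the AEs emerged until 70 days after the last dose are intended". On columns it says: "The TEAEs will be summarized by treatment group and E6011 overall".

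**Laboratory values.** Markedly abnormal values (TEMAVs) are defined in SAP 5.6.3 and 13.2: "Except for phosphate, a TEMAV is defined as a postbaseline value with an increase from baseline to a grade of 2 or higher". The worst-value shift tables use the "LNH classification for the highest and lowest value during the study".

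**Population and switch.** The Safety Analysis Set (SAP 5.2.1) requires a dose and a safety assessment between Weeks 24 and 104. That selects subjects; it does not limit which of their events or weeks are counted. Protocol Table 4, note g, makes the Week 24 dose the first open-label one. The SAP mentions the placebo group's switch at Week 24 only in the mTSS imputation rule (5.3.5).

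**The concern.** A subject randomized to placebo who enters the extension has 24 weeks on placebo and then up to 80 weeks on E6011. With every anchor at the first study-drug dose, that subject's exposure, TEAE status, TEMAVs and worst-value shifts all run from the first placebo injection. The column for this group then mixes two treatments, and the pooled E6011 column may do the same, since nothing says who is in it or from when.

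Safety and tolerability is a primary objective, and the extension supplies the long-term E6011 data. A column that cannot be read as experience on E6011 weakens what the extension is there to show.

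**Working it through.** **1. Reproduce the planned durations.** The protocol synopsis gives 24 weeks of Treatment Phase and 80 weeks of Extension Phase. Protocol 9.4.1 has doses at Weeks 0, 1, 2 and every 2 weeks to Week 22, then every 2 weeks from Week 24 to Week 102. The SAP 5.6.1 formula gives:
- Treatment Phase: (22×7 + 14)/7 = 24 weeks.
- Extension Phase: ((102 − 24)×7 + 14)/7 = 80 weeks.

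Both match, so the formula works when the first dose is the first dose of the treatment in question.

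**2. Apply it literally to a placebo-randomized subject.**

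| Last dose | From first study-drug dose | From first E6011 dose | Ratio |
|---|---|---|---|
| Week 102 | (102×7 + 14)/7 = 104 weeks | 80 weeks | 1.30 |
| Week 52 | (52×7 + 14)/7 = 54 weeks | (28×7 + 14)/7 = 30 weeks | 1.80 |
| Week 36 | (36×7 + 14)/7 = 38 weeks | (12×7 + 14)/7 = 14 weeks | 2.71 |

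The gap is always 24 weeks, so its share grows for those who leave early.

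**3. Injections.** Protocol 9.4.2 supplies 5 + 8 = 13 double-blind administrations. The extension has (102 − 24)/2 + 1 = 40, so the total is 53. SAP 5.6.1 counts records with a non-zero treatment. Protocol Table 1 describes placebo vials as 0 mg/mL, so it is unclear whether placebo injections count. If they do not, a fully compliant completer scores 40/53 = 75% or 40/40 = 100%, depending on the expected number, which the SAP does not define.

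**4. Extension-only reading.** Suppose only events and values from Week 24 onward are meant. Exposure becomes 80 weeks and placebo-period events drop out, but baseline under SAP 8.1.1 is still the value before the first placebo dose. Take a laboratory value below Grade 2 at Week 0 that reaches Grade 2 at Week 12 on placebo and is unchanged at Weeks 24 and 28. Against the Week 0 baseline, Week 28 is a rise to Grade 2 and meets the TEMAV definition. Against the Week 24 predose value there is no rise. Worst-value shifts and worsening-based TEAE status behave the same way. The documents give no rates from which to size this.

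**5. The pooled column.** It appears once, for TEAEs, reported as number and percentage of subjects. At planned group sizes, with everyone entering, the denominator is 25 + 50 + 50 = 125 if ex-placebo subjects are left out and 175 if they are included. If they are included with events from Week 0, the numerator contains placebo-period events.

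**6. Start-date imputation (SAP 8.3.3).** A start date with only the day missing is compared with the month of the first dosing date or, if earlier, of the imputed end date. In any other month it is set to the 1st. If first dosing means Week 0, such an event in the month of the first E6011 dose is set to the 1st, normally before that dose. For the other extreme the rule is: "Completely missing: First dosing date or imputed AE end date, which is earlier".

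**The case against.** The strongest reply is that the SAP is an extension plan and should be read as one. SAP 3 says it covers the Extension Phase, 5.2.1 builds its sets on Weeks 24 to 104, 5.2.2 limits disposition to that phase, and 5.3.5 takes the last observation by phase. On that reading step 2 disappears. This is a fair guess at intent. However, SAP 5.2.1 writes the week limits out, whereas 5.6.1 to 5.6.3 and 8.1.1 do not, and the baseline problem in step 4 remains.

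Second, one prerandomization baseline is a defensible choice for tables by randomized group, which is how Protocol 9.7.1.9 reports the extension. That stands for by-visit tables, where the visit itself separates placebo from E6011 time. It does not settle whether an event is emergent on E6011. SAP 5.6 also says data are summarized as treated, but not how that applies to a subject who switches.

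Third, the programming specifications and table shells (SAP 9 and 11) are separate and may define these terms. That also stands, and it limits confidence in the finding.

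Three stronger readings are tempting and are not supported:
- *The SAP gives no start for safety at all.* It does: Day 1 in SAP 5.6 and the during-treatment condition in 5.6.2. What is missing is a start specific to E6011.
- *The SAP would report 104 weeks of E6011.* Section 5.6.1 calls its result exposure to study drug, by treatment group. It overstates E6011 exposure only if read or pooled as such.
- *A fixed share of pooled E6011 time is placebo.* No pooled exposure or person-time output is planned, so such a percentage would describe nothing the SAP produces.

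**Conclusion.** The point holds as a defect in definitions. Read literally, each completing placebo-randomized subject is credited 104 weeks against 80 on E6011, and placebo-period events sit with E6011 events in that group's column. This rests on the planned schedule, with the last dose at Week 102; the ratio is larger for early leavers. The statement in Protocol 7 that all subjects had completed 52 weeks on E6011 by March 2019 sets no lower bound, because dosing continues to Week 102 and the statement may not describe those who left earlier.

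If the extension-only reading is intended, the remaining fault is the pre-placebo baseline, whose effect cannot be computed. On either reading the pooled TEAE column is undefined and could include placebo-period events. The analyses are descriptive and open-label, by-visit tables are largely unaffected, and the unseen specifications may settle part of this. The change should be made, but it does not threaten the primary efficacy result.

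**What to change.** 1. For placebo-randomized subjects, start E6011 exposure, actual and expected injections, TEAE status, TEMAVs and worst-value shifts at the first E6011 dose (Week 24). Use the last value before that dose as safety baseline. Protocol Table 4 already schedules laboratory tests, vital signs, ECG, chest x-ray, neurological findings and CD4 counts at Week 24, and note a places them before dosing.
2. Define E6011 overall so that it counts no placebo-period events. The simplest form is the SAP 5.2.1 entrants with events from the Week 24 dose onward. Do not combine that set with events from Week 0: besides admitting placebo-period events, it would count the first 24 weeks only for E6011-randomized subjects who stayed to enter the extension.
3. Keep the tables by randomized group, and state in each column the period and baseline used.
4. In SAP 8.3.3, for placebo-randomized subjects, re-anchor only day-missing dates in the month of the first E6011 dose, keeping the earlier imputed end date where there is one. Leave year-only and completely missing dates under a stated convention that does not by default move placebo-period events to E6011.

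Rates per person-year and a wider set of everyone ever dosed with E6011 are optional. If the specifications or shells already contain these definitions, citing them in the SAP is enough.

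The cost is a few definitions and some reprogrammed tables; no new data are needed. The ex-placebo column will have a different baseline from the E6011 columns, and the pool will combine early E6011 exposure (ex-placebo subjects) with later exposure (E6011-randomized subjects). Both must be labelled.
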